
1. Participants will complete Virtual Visit 2 between 1 and 21 days after completing In-Person Lab Visit 1. Virtual Visits 2-5 will ideally be conducted four days in a row to reduce online task fatigue. However, visits may be scheduled up to 7 days apart.

The following assessments will be administered as an interview and entered into REDCap by the interviewer:

1. Timeline Follow Back (TLFB) Questionnaire, which will assess tobacco and nicotine product use since their last virtual visit.

The following surveys will be self-administered using REDCap:

1. Minnesota Nicotine Withdrawal Scale
2. Questionnaire of Smoking Urges-Brief – Usual Brand Cigarette

Participants will complete the ETM task on the computer. If the participant needs assistance with navigating the online marketplace the research staff may screen share and allow the participant to verbally select the items that they would like to purchase. The products available on the ETM include:

- Menthol and non-menthol cigarettes (matched to the participant's preferred brand)
- Fruit, dessert, mint, menthol and tobacco e-liquids (e.g., Suorin iShare)
- Mint, fruit, and cinnamon nicotine gum (e.g., Nicorette).

Participants will undergo one of four marketplace conditions during Virtual Visits 2-5, with the order of administration randomized across participants.

- Marketplace Condition 1 includes only tobacco e-liquids.
- Marketplace Condition 2 includes menthol and tobacco e-liquids.
- Marketplace Condition 3 includes mint menthol, and tobacco e-liquids.
- Marketplace Condition 4 includes fruit, dessert, mint, menthol, and tobacco e-liquids.

Staff will instruct participants to complete the ETM task as if they are purchasing the products from a retailer, and that one iteration of the task will be randomly selected and will determine which products they will use during the field assessment. In reality, we will randomly assign which condition is used 1, 2, 3, or 4 but will assign products based on when menthol cigarettes were not available each to simulate a menthol cigarette ban.

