Sample Size/Estimation/Analysis

Power calculation

Based on prior ETM studies in which the effects of increasing cigarette price were observed in 22-40 participants, a sample size of 80 will be sufficient for answering Aims 1 and 2 as well as the exploratory racial subgroup analyses. No ETM studies have examined the impact of e-liquid flavor availability on combusted tobacco purchasing, so we do not have a direct effect size estimate for our manipulation. In our pilot study, the marketplace manipulation (menthol little cigars available vs. not) resulted in a small effect size (Cohen's $d = 0.31$), likely because JUUL pods were overwhelmingly preferred. When comparing mean menthol/mint e-liquid purchasing vs mean tobacco e-liquid purchasing, there was a large effect size ($d = 1.2$). Thus, we anticipate that our proposed marketplace manipulation will be associated with at least a medium effect size ($d = 0.5$) for non-menthol cigarette purchasing and a sample size of 80 will be sufficient for detecting differences.

For Aim 1 comparing within-participant impact of menthol e-liquid availability on mg of nicotine purchased, our proposed sample size of 80 will have 80% power to detect differences as small as $d=0.31$ using a paired t-test assuming type I error set to 0.05.

Aim 2 hypothesizes that nicotine purchased will be nearly equivalent when mint e-liquid is available or not. Framing the question as an equivalence test, we set a region of equivalence to be [-0.33, 0.33] standard deviations for the difference in effect with the addition of mint. Employing a paired t-test with type I error set to 0.05, our planned sample size of 80 will have 80% power to reject the null that there is an effect outside of [-0.33, 0.33] in favor of the alternative that the effect lies in [-0.33, 0.33]. In the context of mg of nicotine, this would map to an equivalence region of [-20, 20] mg of nicotine, assuming a standard deviation of 60 mg. In other words, we are sufficiently powered to conclude equivalence between mg of nicotine purchased with and without mint available.

Statistical analysis plan

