Linear mixed-effects models with fixed effects for marketplace condition ('tobacco' vs 'menthol & tobacco' vs 'menthol, mint & tobacco') and order of condition administration, and a random effect for participant (to adjust for correlation induced by repeatedly measuring the same participant) will compare the total amount of non-menthol cigarettes and e-liquids purchased at the highest menthol price (Aims 1 and 2). All products will be converted to mg of nicotine (as listed on their packaging) to standardize purchasing across products, as in previous ETM studies.⁵³⁻⁵⁵ Analyses will be conducted to determine if race moderates product purchasing (Exploratory Aim).

ETM data will be used to generate demand curves for each product using an exponential demand equation. Alpha is the rate of change in demand, Q_0 is peak consumption, C is cost, and k is a constant.

Cross-price elasticity estimates will be calculated as the slope of the regression line (B_1) fit to log-transformed purchasing of each alternative product when offered at fixed prices (C) versus log-transformed menthol cigarette price (P): $\log C = B_0 + B_1 \log P$. Exploratory paired t-tests will compare product purchasing during the pre- and post-field assessment ETM task.

For the qualitative data, we will use grounded theory to develop hypotheses related to the topics of interest. Interviews will be audio-recorded and transcribed verbatim. Audio transcriptions will be reviewed for accuracy and entered into Atlas.ti or another qualitative data management software program. Two research staff members will code the first five interviews to achieve greater than 90% interrater reliability and then every 10th interview to ensure integrity. The research team will analyze the interviews using iterative analyses including qualitative research techniques of open and axial coding; major thematic categories; analytical domains; triangulation of data; comparisons within and between groups; and documenting analytical pathways. Saturation will be achieved when no new themes emerge.

HUMAN SUBJECTS PROTECTION

Recruitment Methods

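### A single participant random effect pools one error variance over all condition contrasts; this cannot hold for mint e-liquid analysed by flavor, and the paired-t power for Aims 1 and 2 carries over only if the difference SDs are equal

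*Combined protocol and SAP*

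**What the plan says.** **Analysis.** The Statistical analysis plan section specifies linear mixed-effects models with "fixed effects for marketplace condition ('tobacco' vs 'menthol & tobacco' vs 'menthol, mint & tobacco') and order of condition administration", plus "a random effect for participant (to adjust for correlation induced by repeatedly measuring the same participant". The models "will compare the total amount of non-menthol cigarettes and e-liquids purchased at the highest menthol price (Aims 1 and 2"). No residual covariance structure, random condition effect, robust standard error or sensitivity analysis is named.

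**Power.** The Power calculation section uses a different test. Aim 1 is said to have "80% power to detect differences as small as $d=0.31$ using a paired t-test assuming type I error set to 0.05". For Aim 2, "we set a region of equivalence to be [-0.33, 0.33] standard deviations for the difference in effect with the addition of mint", and the test is stated as "Employing a paired t-test with type I error set to 0.05", with 80% power at n = 80. The margin is translated to ±20 mg of nicotine with an SD of 60 mg. That is the only SD given; there are no condition-specific SDs or correlations.

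**Design.** Under Virtual Visits 2-5, "Marketplace Condition 1 includes only tobacco e-liquids"; Condition 2 adds menthol and Condition 3 adds mint. The Secondary Outcomes list tobacco, menthol and mint e-liquid purchases as separate outcomes.

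**The concern.** A random intercept with independent, equal-variance residuals gives every condition the same variance and every pair of conditions the same correlation. Every pairwise contrast then receives the same standard error. A paired t-test uses the spread of its own differences. The power and analysis sections therefore describe two different tests, and nothing in the plan links them.

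This matters most for Aim 2, which is an equivalence claim. If the mint differences are less variable than the pooled figure, the model's interval is too wide and the trial can miss equivalence at the planned size. A contrast that is more variable than the pooled figure gets too small a standard error and too many false positives. For a flavor that some conditions do not sell, purchases in those conditions are fixed at zero with no variance, and pooling them with real purchasing data distorts the standard errors.

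**Working it through.** **Inputs from the documents.** n = 80 completers; three modelled conditions; Aim 1 d = 0.31; Aim 2 margin ±0.33 SD, or ±20 mg with SD 60 mg; alpha 0.05. **Assumptions.** Two-sided alpha for Aim 1; 0.05 per side for Aim 2 with a true difference of 0; complete data; normal outcomes; no order term in the simulations. Aim 1 is Condition 1 v 2 and Aim 2 is Condition 2 v 3.

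**Step 1: the plan's own figures.** The exact paired t-test at d = 0.31 has 78.2% power (normal approximation 79.2%; exact 80% needs d = 0.317). The paired equivalence test with margin 0.33 SD has 80.0% power. Both stated figures reproduce as paired tests to within 2 points.

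**Step 2: what the random-intercept model uses.** With balanced data and three conditions, the model's variance for any pairwise difference is the mean of the three pairwise difference variances:

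pooled variance = (SD12² + SD23² + SD13²) / 3

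The standard error is the square root of (pooled variance / 80), on about 2 × 79 = 158 degrees of freedom.

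**Step 3: Aims 1 and 2.** Hold SD23 at the plan's 60 mg, set SD12 = SD13 = s (assumed), and use a margin of 20 mg. For s = 80 the pooled variance is (6400 + 3600 + 6400)/3 = 5467, so the pooled SD is 73.9. The Aim 1 standard error is then 73.9/80 = 0.92 of its true value, and the Aim 2 standard error is 73.9/60 = 1.23 times its true value. The last two columns are from simulation.

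| s (mg) | Pooled SD | Aim 1 SE ratio | Aim 2 SE ratio | Aim 1 type I error | Aim 2 equivalence power |
|---|---|---|---|---|---|
| 50 | 53.5 | 1.07 | 0.89 | about 3.6% | about 87% |
| 60 | 60.0 | 1.00 | 1.00 | about 5% | about 81% |
| 70 | 66.8 | 0.95 | 1.11 | about 6% | about 74% |
| 80 | 73.9 | 0.92 | 1.23 | about 7% | about 65% |
| 90 | 81.2 | 0.90 | 1.35 | about 7.6% | about 54% |
| 100 | 88.7 | 0.89 | 1.48 | about 8% | about 41% |

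The 81% at s = 60 exceeds 80.0% mainly because 20/60 = 0.333 is slightly wider than 0.33. In every row, contrast-specific standard errors gave about 5% and about 81%.

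**Step 4: sensitivity to the third SD.** Let the Aim 1 and Aim 2 differences be uncorrelated, so that SD13² = SD12² + SD23².
- SD12 = 80: SD13 = 100, pooled SD = √(20000/3) = 81.6. Type I error is about 4.7% and Aim 2 power about 53%.
- SD12 = 90: SD13 = 108.2, pooled SD = √(23400/3) = 88.3. Type I error is 5.3 to 5.5% and Aim 2 power about 41%.
- SD12 = SD23 = 60: SD13 = 84.9, pooled SD = √(14400/3) = 69.3, so both standard errors are 1.155 times too large. Aim 1 power at d = 0.31 is about 69% and Aim 2 power at 0.33 SD about 70%. Equality of the two named contrasts alone is therefore not enough; all three SDs must match.

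**Step 5: mint e-liquid by flavor.** Purchases are zero in Conditions 1 and 2, with variance s² in Condition 3. The difference variances are 0 (1 v 2), s² (1 v 3) and s² (2 v 3), with mean 2s²/3. The model's standard error for 2 v 3 is √(2/3) = 0.816 of the true one, whatever s is. The nominal 95% interval reaches 1.975 × 0.816 = 1.61 true standard errors, and simulated coverage is about 89%. The 1 v 2 contrast, zero by construction, gets the same non-zero standard error.

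**Step 6: menthol e-liquid by flavor.** Zero in Condition 1; assume equal variance s² and correlation r in Conditions 2 and 3. The difference variances are s², s² and 2s²(1 − r), with mean s²(4 − 2r)/3.
- r = 0.5: the mean is s², and all standard errors are right.
- r = 0.8: the mean is 0.8s². The 1 v 2 SE is √0.8 = 0.89 of true; the 2 v 3 SE is √(0.8/0.4) = 1.41 times true.
- r = 0.3: the mean is 1.133s². The 1 v 2 SE is 1.06 times true; the 2 v 3 SE is √(1.133/1.4) = 0.90 of true.

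Tobacco e-liquid is sold in every condition and has no forced zeros.

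**The case against.** **The documents give no evidence of unequal variances.** This is correct. Only one SD is stated, and if all three difference SDs equal 60 mg the planned model gives 78.7% for Aim 1 and 80.5% for Aim 2, so the paired-t power does carry over. A reader might infer from the hypotheses (an effect for Aim 1, almost none for Aim 2) that the Aim 1 and Aim 2 error bars are wrong. That does not follow. The plan anticipates at least a medium effect (d = 0.5) for non-menthol cigarettes; its d = 1.2 concerns e-liquid purchasing, a different outcome. A larger mean shift also does not establish a larger SD of differences. Wider spread in Aim 1 is plausible if smokers respond very differently to menthol e-liquid, but it is not shown.

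**The type I inflation depends on the assumed pattern.** This stands too. Setting SD13 equal to SD12 implies a negative correlation between the two differences, and with uncorrelated differences the inflation nearly vanishes (Step 4). The loss of Aim 2 power remains in those cases, but still under assumed SDs.

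**Silence on covariance does not exclude a better structure.** True, but the only device named for within-participant correlation is the participant effect. If something richer is intended, the plan should state it.

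**The e-liquids might be summed over flavors.** There would then be no forced zeros, because tobacco e-liquid is always sold. The Secondary Outcomes, however, list the flavors separately. Mint sold against mint not sold is also a secondary comparison against a known zero, not an Aim, which limits what is at stake there.

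**Conclusion.** The point holds in two parts of different strength.

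- **Certain by design, if flavors are modelled separately as listed and the random effect is an ordinary intercept.** Mint e-liquid cannot meet the equal-variance assumption. Its Condition 2 v 3 standard error is 0.82 of the true value, with about 89% coverage. Menthol e-liquid can err in either direction. It would be wrong to conclude that all e-liquid intervals are too narrow: the mint 1 v 2 interval is too wide, the menthol 2 v 3 standard error can be 1.41 times too large, and tobacco e-liquid has no forced zeros.
- **Conditional for Aims 1 and 2.** The power section and the model agree only under equal difference SDs, which the plan neither states nor supports. Over the assumed 50 to 100 mg range, Aim 2 equivalence power runs from about 87% to 41% and Aim 1 type I error from about 3.6% to 8%. These figures show sensitivity; they are not estimates of error in this trial.

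The plan should be changed, because the power claims currently describe a test that it does not specify.

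**What to change.** For the Aim 1 and Aim 2 contrasts, keep the mixed model for the means but specify an unstructured within-participant covariance with Kenward-Roger degrees of freedom. Robust standard errors, or within-participant differences adjusted for session, would also serve. State in the Power calculation that the paired-t figures refer to these contrast-specific tests.

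Compare each flavored e-liquid only across conditions that sell it. In the three-level model as written, menthol is compared between Conditions 2 and 3. Mint is sold in one modelled condition only and should be reported descriptively, since no structure with a zero-variance cell can be fitted sensibly.

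**Cost.** A sentence or two of SAP wording, with no change to recruitment, visits or data. A three-condition unstructured covariance has six parameters, readily estimated from 80 participants. Error degrees of freedom fall from about 158 to about 79. If the variances prove equal, the power loss is negligible (about 81% for Aim 2 either way).

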2. Self-report smoking at least 5 cigarettes per day for the past year
3. Self-report smoking menthol cigarette brands > 80% of the time
4. Breathe carbon monoxide (CO) level > 8 ppm or positive urine NicCheck
5. Willingness to use other tobacco products during the study
6. Speak, comprehend, and read English sufficiently to complete study procedures
7. Have home access to a computer, smart phone, or tablet with a web camera and internet access

Exclusion criteria:

1. Currently seeking treatment to quit smoking
2. Self-reported serious medical or psychiatric condition(s) including cardiovascular and chronic respiratory diseases
3. Body temperature > 100.4 F

4. Cold, flu or COVID-19 symptoms including fever, cough, and runny nose in the past 30 days
5. Currently pregnant, breastfeeding or intending to become pregnant for the duration of the study or unwilling to agree to use adequate protection to avoid pregnancy
6. CO reading > 80 ppm
7. Enrollment stratum (Non-Hispanic, white or Black/African American)

Individuals who report smoking non-menthol flavored cigarettes will be excluded since the purpose of the trial is to understand how menthol and mint e-liquid flavor restrictions affect menthol cigarette smokers. We plan to enroll equal numbers of white and African-American/Black participants so we will exclude individuals once the stratum is full (i.e. 40 enrolled). Those with unstable medical or psychiatric conditions are excluded as these symptoms could affect a participant's ability to complete the study. We will exclude those indicating immediate readiness to stop smoking, as participation in this study may not lead to reductions in smoking. We will exclude pregnant people, those trying to become pregnant and those currently breastfeeding due to the potential harmful effects of tobacco use on developing fetuses and infants. Because participants are required to complete portions of the protocol independently during the virtual lab sessions, they will need to be able to independently read and comprehend the study materials.

Those who report past 30 day cold, flu or COVID-19 symptoms will be temporarily excluded as a safety precaution. They will be able to re-screen once they have been symptom-free for more than 30 days.

Telephone Screening Survey

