For each marketplace condition, participants will complete 10 iterations of the ETM task in ascending order. The prices for menthol cigarettes on the ETM will be set at: \$0.12, \$0.25, \$0.50, \$1.00, \$2.00, \$4.00, \$8.00, and \$16.00 and \$32.00 per cigarette. During one task iteration, menthol cigarettes will be eliminated from the marketplace to simulate a menthol cigarette ban. The costs for the other products will reflect average prices in NC and will not change during the task. For each task iteration, participants will receive individually-tailored account balances approximately equal to the money they would spend on cigarettes for seven days. They can

purchase as many or few products as their account balance allows. Participants are not required to buy products from the ETM or can buy nicotine gum if they prefer to abstain. If they do not buy products from the ETM and do not use tobacco products during the field assessment (biochemically-verified), then they will receive their ETM account balance at Virtual Visit 6. This payment is delayed to reduce the likelihood that they will use this money to buy their preferred brand menthol cigarettes, thus decreasing the validity of the ETM task.

Participants will be instructed to use only the products purchased from the ETM during the subsequent 7-day period after Virtual Visit 5 and told that we will assess adherence by self-report, product accountability, and biochemical verification. The field assessment validates the ETM task by having participants use the products in the real world, simulating the different regulatory environments. Actual product use enables us to measure their subjective experiences such as withdrawal, craving, or product satisfaction as well as assess changes in carbon monoxide exposure, a biomarker of harm, when using products other than menthol cigarettes. We will conduct between-subjects analyses comparing these secondary outcomes by marketplace condition.

In-Person Lab Visit 2

In-Person Lab Visit 2 will be completed up to 48 hours after completing Virtual Visit 5. Participants will complete the COVID screener within 24 hours of their Lab visit via email or phone. Research staff will wear personal protective equipment during the visit including face masks and gloves. The participants will be required to wear facemasks when interacting with the staff. Temperature checks will be conducted immediately upon arrival using a thermal heat scanner.

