All participants will be emailed a cessation manual and local smoking cessation resources.

Product adherence

To verify self-reported tobacco use, all used and unused products will be collected and counted at In-Person Lab Visit 3. Discrepancies between consumption stated on the TLFB versus consumption based on the products returned will be addressed. Non-adherence (i.e., using products not purchased from the ETM) will be assessed via the TLFB and qualitative interview with the importance of honest self-reporting emphasized. If participants report not using combusted tobacco, then CO readings < 6 ppm will verify their self-report.

Compensation

Participants will be paid \$155 for completing the study. They will earn \$30 for completing Virtual Visit 1, \$15 per visit for completing Virtual Visits 2-6 plus a \$50 bonus for completing the study.

Participants that do not meet enrollment criteria at Virtual 1 will earn \$20 for attending the visit. Participants that start but do not complete the study will receive payments for the virtual visits attended. They will not receive the \$50 completion bonus.

ANALYSIS PLAN

Primary Outcome

Protocol Version 10
5.13.22

- Total amount of non-menthol cigarettes purchased when menthol cigarettes are not available.

Secondary Outcomes

- Total amount of tobacco e-liquid purchased when menthol cigarettes are not available.
- Total amount of menthol e-liquid purchased when menthol cigarettes are not available.
- Total amount of mint e-liquid purchased when menthol cigarettes are not available.
- Total amount of dessert and fruit e-liquid purchased with menthol cigarettes are not available

Exploratory Outcomes

- Mean Perceived Health Risk Scale scores
- Mean Product Evaluation Scale scores
- Mean Minnesota Nicotine Withdrawal Scale scores
- Mean Questionnaire on Smoking Urges scores
- Mean Tobacco Product Interest scores
- Mean Tobacco Policy Questionnaire scores
- Total amount of non-menthol cigarettes purchased when menthol cigarettes are not available by race
- Total amount of tobacco e-liquid purchased when menthol cigarettes are not available by race.
- Total amount of menthol e-liquid purchased when menthol cigarettes are not available by race.
- Total amount of mint e-liquid purchased when menthol cigarettes are not available by race.
- Total amount of dessert/fruit e-liquid purchased when menthol cigarettes are not available by race.
- Themes emerging from the qualitative interviews

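### The Aim 1 and 2 model is set at the top menthol price, but the primary outcome is purchasing with menthol cigarettes off the market, so read literally the declared primary outcome has no specified analysis

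*Combined protocol and SAP*

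**What the plan says.** All references are to the combined protocol and SAP.

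- **Outcome.** Under Primary Outcome: "Total amount of non-menthol cigarettes purchased when menthol cigarettes are not available". The four e-liquid secondary outcomes and the five by-race purchasing outcomes carry the same condition.
- **Model.** The Statistical analysis plan specifies linear mixed-effects models with fixed effects for marketplace condition (three levels) and order, and a random participant effect. These will "compare the total amount of non-menthol cigarettes and e-liquids purchased at the highest menthol price (Aims 1 and 2", with products converted to mg of nicotine.
- **Task.** Virtual Visits 2-5 sets ten iterations per marketplace condition and lists menthol prices from $0.12 to $32.00 per cigarette. It then adds: "During one task iteration, menthol cigarettes will be eliminated from the marketplace to simulate a menthol cigarette ban". At each iteration "participants will receive individually-tailored account balances approximately equal to the money they would spend on cigarettes for seven days".
- **Field assessment.** The same section says that staff "will assign products based on when menthol cigarettes were not available each to simulate a menthol cigarette ban".
- **Other task analyses.** The Statistical analysis plan also has demand curves, and a cross-price regression of log-transformed "purchasing of each alternative product when offered at fixed prices (C) versus log-transformed menthol cigarette price (P". It adds exploratory pre/post paired t-tests and a sentence on moderation by race.

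**The concern.** The outcome definition and the model sentence point to different rows of the dataset. An analyst working from the outcome list would take the menthol-free iteration, and one working from the model sentence would take the $32.00 iteration.

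Three things are at stake:

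- **The question answered.** The effect of flavor availability under a simulated menthol ban is not the same quantity as its effect when menthol cigarettes are very expensive but still on sale.
- **The link to the field assessment.** That phase is meant to validate the task and supplies the products chosen in the menthol-free iteration. A primary analysis at $32.00 would rest on a different basket.
- **Pre-specification.** Both iterations are collected in every condition, so the choice between them could be made after results are seen. This matters most for Aim 2, whose conclusion depends on whether a difference lies within [-20, 20] mg of nicotine.

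**Working it through.** **1. Are the two iterations distinct?** The price list in Virtual Visits 2-5 is $0.12, $0.25, $0.50, $1, $2, $4, $8, $16 and $32, which is 9 prices. Adding the one iteration with menthol removed gives 9 + 1 = 10, the stated number. The top price and the ban are therefore different iterations.

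**2. Does any other planned analysis cover the primary outcome for Aims 1 and 2?**

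| Analysis | Covers it? | Reason |
|---|---|---|
| Mixed model | No, as written | Names the top menthol price |
| Demand curves | No | Need a cost; menthol has none when it is not sold |
| Cross-price regression | No | Regresses on log menthol price, undefined in the ban iteration |
| Pre/post t-tests | No | Exploratory; compare time points, not marketplace conditions |
| Moderation by race | No | Names no iteration; serves only the Exploratory Aim |
| Paired t-tests under Power calculation | No | Basis for sample size only; name no iteration |

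**3. Do the stated power figures depend on the choice?** With N = 80, d = 0.31 and two-sided 0.05, paired t-test power is 78.2% (noncentral t) or 79.2% (normal approximation), against the stated 80%. For Aim 2, two one-sided tests at 0.05 each, with a margin of 0.33 SD and a true difference of 0, give 80.1% (simulated t) or 80.9% (normal), again against 80%. The mg margin agrees: 20/60 = 0.333 SD. These figures are in SD units, and neither they nor the 60 mg SD are tied to an iteration, so they do not change.

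**4. When could purchasing differ between the two iterations?** Other prices are fixed and the balance is set individually. The affordable baskets differ only if the balance covers at least one $32 menthol cigarette. The document gives no usual price, so a range is assumed, with single-cigarette sale.

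Threshold in cigarettes/day = 32 / (7 × usual price per cigarette):

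- $0.50: 32 / 3.50 = 9.14
- $0.35: 32 / 2.45 = 13.06
- $0.25: 32 / 1.75 = 18.29

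Entry requires "Self-report smoking at least 5 cigarettes per day for the past year". At 5 a day the balance is 5 × 7 × $0.25 = $8.75 to 5 × 7 × $0.50 = $17.50. Both are below $32, so the affordable baskets are identical in the two iterations.

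For an assumed 20-a-day smoker, the balance is 20 × 7 × $0.50 = $70 or 20 × 7 × $0.35 = $49. One $32 cigarette would take 32/70 = 46% or 32/49 = 65% of it, but only if the participant chose to buy it.

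If menthol cigarettes could be bought only in packs (20 assumed), the smallest purchase would be 20 × $32 = $640. At $0.50 that needs 640 / 3.50 = 183 cigarettes a day, so in effect nobody's affordable basket would differ.

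**5. Which outcomes would a corrected iteration reach?** The model's condition term has 3 of the 4 marketplace conditions. Tobacco e-liquid is sold in 3 of these 3, menthol in 2, mint in 1, and dessert and fruit in 0, because those two flavors appear only in the fourth: "Marketplace Condition 4 includes fruit, dessert, mint, menthol, and tobacco e-liquids".

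**The case against.** The strongest reply is that this is a slip in one qualifier, not a missing analysis. The plan gives the model, variable, scale, effects and aims; only the iteration is off. There is some support for reading the top price as the ban. The ten iterations are said to run in ascending order with only nine prices, so the ban would naturally sit at the top. The Behavioral Economics section treats price as analogous to the effort of obtaining a product, which makes unavailability the limit of price. The outcome list and the assignment of field products both point to the ban, and the by-race outcomes are defined on it. The practical effect may also be very small: few people would spend $32 on one cigarette, and under pack-only sale none could.

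Much of this stands. Loose wording is plausible, the numerical effect may be negligible, and no bias has been shown. But no section equates the two iterations, and the task description separates them. The by-race outcomes serve only the Exploratory Aim. Similar expected results do not settle which data the primary analysis uses; the plan has to. The mint and dessert/fruit gap is a side issue, and the conclusion does not rest on it.

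**Conclusion.** The concern holds. The model sentence is wrong as written, because it places the Aim 1 and 2 comparison at $32.00 while the primary outcome is measured with menthol cigarettes removed. This must be reconciled before analysis. That conclusion comes from the text and the iteration count alone and needs no assumption.

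The size of any numerical difference cannot be computed, since the document gives neither usual prices nor a distribution of smoking rates. The thresholds of 9.14, 13.06 and 18.29 cigarettes a day assume usual prices of $0.50, $0.35 and $0.25 and single-cigarette sale. They are necessary conditions only: a participant above them must also choose to buy at $32. Pack-only sale would take the affected share to essentially zero.

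**What to change.** - **Main change.** In the mixed-model sentence of the Statistical analysis plan, replace the reference to the top menthol price with the task iteration from which menthol cigarettes have been removed. This aligns the model with the primary outcome, with the tobacco and menthol e-liquid outcomes, and with the basket used in the field assessment.
- **Optional.** Keep the $32.00 iteration as a labelled sensitivity analysis.
- **Separate statement.** Say how the mint and the dessert/fruit outcomes will be analysed. Mint is sold in only one modelled condition, so its comparison there is against zero by design. Dessert and fruit are sold in none of the modelled conditions.

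The cost is one sentence of SAP wording for the primary outcome and a short statement for the two e-liquid outcomes. Both iterations are already collected, and neither the sample size nor the equivalence margin changes. The change should be dated before the purchasing data are examined by condition.
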